6.3. Sample Size Justification

Approximately seventy-five (75) subjects at up to eight (8) active sites will be enrolled in the CVT-SFA Trial. All subjects will be scheduled for clinical examination and duplex ultrasonography assessment at six (6) months. The objective of the study is to assess the initial feasibility and performance of the CVT Everolimus-coated Catheter in the treatment of subjects with *de-novo* occluded/stenotic or re- occluded/restenotic superficial femoral (SFA) or popliteal arteries. The study is powered based on primary safety and effectiveness endpoints.

The primary safety endpoint for this analysis is freedom from Major Adverse Event (ffMAE, %) at six (6) months post-procedure. The null (H_0) and alternative (H_A) hypotheses are:

```
H0: ffMAE historical control ≤ ffMAE CVT treatment
HA: ffMAE historical control > ffMAE CVT treatment
```

The proposed sample size of N=75 is based on the primary safety endpoint of freedom from MAE at 6 months. The sample size calculation is based on the following assumptions:

- A single comparison of CVT Everolimus-coated PTA Catheter treatment group to a safety OPC.
 - The assumed difference between the OPC and the treatment group is 15%. This assumption is made based on the results observed in the control arm of the IN.PACT, STELLAREX, LUTONIX, RANGER programs³
 - \circ One-tailed α =0.025

The primary effectiveness endpoint for this analysis is patency (%) at six (6) months. The null (H_0) and alternative (H_A) hypotheses are:

```
H0: Patency historical control ≤ Patency CVT treatment HA: Patency historical control > Patency CVT treatment
```

The sample size of N=75 is based on the primary effectiveness endpoint of patency (%) at six (6) months and the following assumptions:

- A single comparison of CVT Everolimus-coated PTA Catheter treatment group to a patency OPC.
 - The assumed difference between the OPC and the treatment group is 15%. This assumption is made based on the results observed in the control arms of the IN.PACT, STELLAREX, LUTONIX, RANGER programs³
 - o Approximately 10% rate of lost to follow-up or dropout.

Confidential Page 35 of 79

IN.PACT https://www.accessdata.fda.gov/cdrh_docs/pdf14/P140010e.pdf STELLAREX https://www.accessdata.fda.gov/cdrh_docs/pdf16/P160049B.pdf, LUTONIX https://www.accessdata.fda.gov/cdrh_docs/pdf13/P130024S009B.pdf RANGER https://www.accessdata.fda.gov/cdrh_docs/pdf19/P190019B.pdf

\circ One-tailed α =0.025

The primary safety endpoint for this analysis is the freedom from Major Adverse Events at six (6) months. The study is powered based on this primary safety endpoint and the goal is to compare the CVT Everolimus-coated PTA Catheter treated group to an OPC established using a database of historical studies³. Since this is a feasibility trial, hypothesis testing and the attainment of statistical significance when compared to historical control are neither necessary nor sufficient conditions to determine whether the device merits further study. Instead, the focus will be on estimating the frequency of Major Adverse Events at six (6) months post-procedure and the associated 95% confidence interval. The sample size for the study based on the primary safety endpoint of frequency of Major Adverse Events at six (6) months was calculated using the following assumptions:

- A single comparison of CVT Everolimus-coated PTA Catheter treatment group to an historical control group
- An OPC of 70%

Given the above assumptions, enrollment of 75 subjects (safety population) will be the recruitment goal.

If 11 of 75 (15%) subjects experience MAEs, the point estimate for ffMAE is 85% and the 95% CI is [75.3%, 92.4%], well above the OPC of 70%.

The primary effectiveness endpoint for this analysis is patency at six (6) months. The study is also powered on this endpoint and the goal is to compare the CVT Everolimus-coated PTA Catheter treated group to an OPC established using the same database of historical studies as was used above for safety. The sample size for the effectiveness endpoint of patency at six (6) months post-procedure and the associated 95% confidence interval is estimated under the following assumptions:

- A single comparison of CVT Treatment group to an historical control group
- A patency OPC of 65%

Given the above assumptions, enrollment of 75 subjects (yielding ~68 evaluable subjects) will be the recruitment goal.

If as few as 55 of 68 subjects remain patent at 6 months, the point estimate is 81% and the 95% CI is [71.5%, 90.2%], well above the OPC of 65%.

The power estimates from enrolling 75 subjects to detect 15%-point margins above the Safety and Effectiveness OPCs are 85% and 78%, respectively.

Sample size and power calculations were performed using PASS13.

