6. STATISTICAL DESIGN AND ANALYSIS

6.1. Statistical Overview of the Trial

The primary sample size calculation is based on the hypotheses that the primary safety and effectiveness endpoints meet pre-determined Objective Performance Criteria (OPC).

The OPCs for the primary safety and effectiveness endpoints have been determined using historical control data from published studies. Since this is a feasibility trial, the attainment of statistical significance is neither a necessary nor a sufficient condition for determining whether the device merits further study. For example, if the data exhibits a trend ($p \le 0.15$) toward statistical significance when compared to historical control and raises no safety concerns, it may be deemed worthy of further investigation. In addition, there will be a focus on estimating the magnitude of observed rates at 180 days post-procedure and the associated 95% confidence intervals.

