6.4. Statistical Analyses

Detailed analyses of the primary endpoints will be performed when all of the subjects complete their primary follow-up visit at 180 days. No effort will be made to impute or extrapolate data to replace missing values. All calculations will be based on available data with missing data excluded. Any unused or spurious data will be noted as

Confidential Page 36 of 79

appropriate in the final report.

Analysis of Primary Endpoints

The primary effectiveness endpoint of patency at six (6) months will be analyzed on a per-subject basis for the evaluable populations.

The primary safety endpoint of freedom from MAE at 6 months will be analyzed using the safety population.

For both primary endpoints (ffMAE and patency at 6 months), percentages and exact 95% confidence intervals using Clopper-Pearson's method will be calculated.

Analysis of Secondary Endpoints

All secondary endpoints will be analyzed for the per-treatment evaluable population descriptive statistics will be provided to gain better understanding of the data.

For binary variables such as MAE or technical success counts, percentages, and exact 95% confidence intervals using Clopper-Pearson's method will be calculated. For continuous variables, means, standard deviations, and 95% confidence intervals for the mean using the Gaussian approximation will be calculated. If the assumption of normality seems untenable, nonparametric summary statistics will be presented instead.

For time-to-event variables, such as time to target lesion revascularization, survival curves will be constructed using Kaplan-Meier estimates, and log rank test results will be displayed for descriptive purposes only.

Analysis of Other Data

The clinical laboratory values collected will be analyzed by tabulating the number and percentage of subjects with clinically significant changes from baseline for each parameter at each time point.

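### Both primary hypothesis pairs in section 6.3 are printed in the reverse direction and contradict the power statement and worked examples in the same section

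*Combined protocol and SAP*

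**What the plan says.** Section 6.3 sets out a null and an alternative for each primary endpoint at 6 months, with a one-tailed alpha of 0.025.

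- Safety (freedom from MAE): the null is "ffMAE historical control ≤ ffMAE CVT treatment" and the alternative is "ffMAE historical control > ffMAE CVT treatment".
- Effectiveness (patency): the pair has the same form, and the alternative is "Patency historical control > Patency CVT treatment".

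The same section gives a safety OPC of 70%, a patency OPC of 65%, an assumed difference of 15 points, 75 enrolled subjects and about 68 evaluable for patency. It then states: "The power estimates from enrolling 75 subjects to detect 15%-point margins above the Safety and Effectiveness OPCs are 85% and 78%, respectively". Its safety example, with 11 MAEs in 75 subjects, concludes that "the point estimate for ffMAE is 85% and the 95% CI is [75.3%, 92.4%], well above the OPC of 70" percent. The patency example, 55 of 68, is read in the same favourable way against 65%.

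Section 6.1 says the sample size rests on the hypotheses that "the primary safety and effectiveness endpoints meet pre-determined Objective Performance Criteria". It adds, as an example, that a p-value of 0.15 or less showing a trend "toward statistical significance when compared to historical control and raises no safety concerns, it may be deemed worthy of further investigation". For the analysis itself, section 6.4 says: "For both primary endpoints (ffMAE and patency at 6 months), percentages and exact 95% confidence intervals using Clopper-Pearson's method will be calculated".

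**The concern.** Freedom from MAE and patency are both better when higher. With the control's rate greater than the device's rate as the alternative, the result the sponsor hopes for sits in the null, and rejection would be evidence against the device. A one-tailed test is defined by its direction, so the hypotheses as printed and the power as stated cannot belong to the same test.

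Both pairs, and both lines of each pair, are reversed in the same way. That makes a fault in reading the PDF unlikely.

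At stake is whether the pre-specified hypotheses for the two primary endpoints can be used at all. Anyone who programs or audits the comparison from those lines would test the wrong tail. The illustrative p ≤ 0.15 trend in 6.1 also needs a direction before it means anything.

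**Working it through.** **Inputs, all from section 6.3.** Safety: n = 75, OPC 0.70, assumed rate 0.70 + 0.15 = 0.85. Patency: n = 68, OPC 0.65, assumed rate 0.65 + 0.15 = 0.80. One-sided alpha 0.025. X is the number of subjects free of MAE, or patent. Sections 6.3 and 6.4 name no test, so the exact binomial test is taken as the base case because it matches the exact intervals in 6.4.

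**1. Reproducing the stated power (upper tail, H0: p ≤ OPC).**

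The cut-off is the smallest r with P(X ≥ r | OPC) ≤ 0.025, and power is P(X ≥ r | assumed rate).

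- Safety: r = 61 (81.3%). P(X ≥ 61 | 0.70) = 0.0187. Power = P(X ≥ 61 | 0.85) = 0.853, against the stated 85%.
- Patency, exact: r = 53 (77.9%). P(X ≥ 53 | 0.65) = 0.0150, while P(X ≥ 52 | 0.65) = 0.0290 is too large. Power = P(X ≥ 53 | 0.80) = 0.724.
- Patency, normal approximation: cut-off = 0.65 + 1.96·√(0.65·0.35/68) = 0.763. Power = Φ[(0.80 − 0.763)/√(0.80·0.20/68)] = 0.775 (unrounded cut-off), against the stated 78%.

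The stated figures therefore belong to the upper tail. No single one of these two tests gives both at 75 and 68: the normal approximation puts safety power at 86.9%. The exact patency test at n = 75, without dropout, gives 76.9%.

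**2. The hypotheses as printed (lower tail, H0: p ≥ OPC).**

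The cut-off is the largest c with P(X ≤ c | OPC) ≤ 0.025.

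- Safety: c = 44 (58.7%). P(X ≤ 44 | 0.70) = 0.0242. Power at 85% = P(X ≤ 44 | 0.85) = 3.4 × 10⁻⁸.
- Patency: c = 35 (51.5%). P(X ≤ 35 | 0.65) = 0.0148. Power at 80% = P(X ≤ 35 | 0.80) = 1.3 × 10⁻⁷.

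**3. Could the 15 points be a shortfall?** Taking true rates of 55% and 50%, the lower-tail exact power is 77.4% for safety, and for patency 64.2% at n = 68 or 75.6% at n = 75. The stated 85% and 78% are not recovered, and the plan says above, not below.

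**4. The plan's own favourable examples.**

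| Example | p as printed, P(X ≤ x) | p as intended, P(X ≥ x) |
|---|---|---|
| 64/75 free of MAE (75 − 11), OPC 70% | 0.9994 | 0.0017 |
| 55/68 patent, OPC 65% | 0.9987 | 0.0032 |

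**5. The 6.1 trend, if its p-value is one-sided.** In the intended direction, p ≤ 0.15 is reached at 58/75 or more (p = 0.102; 57 gives 0.157) and at 49/68 or more (p = 0.136; 48 gives 0.202). As printed, it is reached at 47/75 or fewer (p = 0.105; 48 gives 0.157) and at 39/68 or fewer (p = 0.117; 40 gives 0.173).

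**The case against.** The strongest reply is that no planned analysis uses the printed direction. Section 6.4 specifies only percentages and exact intervals, with no test or success rule. Sections 6.1 and 6.3 say that significance is neither necessary nor sufficient and that the focus is on estimation. The intended direction is plain from the power statement and the examples, so this is a slip with one sensible reading. On that view the tiny power figures describe a test nobody means to run, and the low cost of a correction is no measure of harm.

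Much of this stands. No estimate, interval or sample size changes. The power figures measure how far the hypotheses are from the power statement, not a risk to a reported result. Section 6.1's wording about meeting the OPC is weak evidence of direction, since the printed null could also be called meeting it; the case rests on 6.3. The 0.15 trend is an illustration, and nothing requires it to be one-sided. The basis of the 78% cannot be settled either, because the plan names the software but not the test.

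What does not stand is the inference that the lines may be left alone. They are the formal hypotheses for both primary endpoints, they carry a one-tailed alpha, and section 6.3 says the study is powered on those endpoints. The intent is clear only because the surrounding text contradicts them.

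**Conclusion.** The concern holds. Both primary hypothesis pairs are inverted relative to the test the trial was powered for, so the one-tailed 0.025 comparison cannot be carried out as printed with the stated power. The exact figures assume a one-sample binomial test at the plan's own OPCs, margins and sample sizes; the direction of the error depends on none of these.

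The correction is required because the pre-specified primary hypotheses say the opposite of what the trial is designed to show. The practical effect is limited: enrolment of 75 stands, and the Clopper-Pearson intervals do not depend on direction.

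**What to change.** Replace the four hypothesis lines in section 6.3 with:

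- Safety: H0: ffMAE(CVT) ≤ 70% against HA: ffMAE(CVT) > 70%.
- Effectiveness: H0: patency(CVT) ≤ 65% against HA: patency(CVT) > 65%.

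In section 6.1, add a clause saying that the illustrative trend p-value is one-sided in this direction. If a two-sided p-value was meant, say that instead and state that the trend must favour the device.

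These edits correct the error. Naming the test at the same time is optional but useful:

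- **Exact binomial test.** This agrees with 6.4, since rejection is equivalent to a two-sided 95% Clopper-Pearson lower limit above the OPC (70.7% at 61/75, 66.2% at 53/68). Safety power stays at 85%, but patency power at 68 evaluable subjects should be restated as about 72%.
- **Normal approximation.** Patency power can stay at 78%, but safety power becomes about 87%. This test also rejects at 52/68, where the exact one-sided p is 0.029 and the Clopper-Pearson lower limit is 64.6%, below the OPC.

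The cost is four lines in 6.3 and one clause in 6.1, plus the power sentence in 6.3 if a test is named. Enrolment, visits, data collection and the planned intervals do not change.

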6.4. Statistical Analyses

Detailed analyses of the primary endpoints will be performed when all of the subjects complete their primary follow-up visit at 180 days. No effort will be made to impute or extrapolate data to replace missing values. All calculations will be based on available data with missing data excluded. Any unused or spurious data will be noted as

Confidential Page 36 of 79

appropriate in the final report.

Analysis of Primary Endpoints

The primary effectiveness endpoint of patency at six (6) months will be analyzed on a per-subject basis for the evaluable populations.

The primary safety endpoint of freedom from MAE at 6 months will be analyzed using the safety population.

For both primary endpoints (ffMAE and patency at 6 months), percentages and exact 95% confidence intervals using Clopper-Pearson's method will be calculated.

Analysis of Secondary Endpoints

All secondary endpoints will be analyzed for the per-treatment evaluable population descriptive statistics will be provided to gain better understanding of the data.

For binary variables such as MAE or technical success counts, percentages, and exact 95% confidence intervals using Clopper-Pearson's method will be calculated. For continuous variables, means, standard deviations, and 95% confidence intervals for the mean using the Gaussian approximation will be calculated. If the assumption of normality seems untenable, nonparametric summary statistics will be presented instead.

For time-to-event variables, such as time to target lesion revascularization, survival curves will be constructed using Kaplan-Meier estimates, and log rank test results will be displayed for descriptive purposes only.

Analysis of Other Data

The clinical laboratory values collected will be analyzed by tabulating the number and percentage of subjects with clinically significant changes from baseline for each parameter at each time point.

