3.1. Primary Endpoints

Primary Safety Endpoint

The primary safety endpoint for the study is freedom of major adverse event (MAE) rate at 6 months post-procedure, defined as a composite rate of cardiovascular death, index limb amputation and ischemia-driven target lesion revascularization (TLR).

Confidential Page 15 of 79

Primary Effectiveness Endpoint

The primary effectiveness endpoint for the study is patency at 6 months post-procedure, defined as freedom from restenosis as determined by duplex ultrasonography (DUS) (peak systolic velocity ratio (PSVR) \leq 2.4 or restenosis \leq 50%) within 6 months and freedom from ischemia-driven target lesion revascularization (TLR).

Restenosis is determined by either PSVR >2.4, as assessed by an independent DUS core laboratory, or >50% stenosis, as assessed by an independent angiographic core laboratory in the event an angiogram has been recorded.

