3.2. Secondary Endpoints

The following endpoints will be also evaluated as secondary endpoints:

- Rate of Major Adverse Event (MAE) Rate in hospital and at 30 days, 1, 2 and 3 years post-procedure, defined as a composite rate of cardiovascular death, index limb amputation and ischemia-driven Target Lesion Revascularization (TLR).
- Rate of occurrence of arterial thrombosis of the treated segment.
- Rate of ipsilateral embolic events of the study limb.
- Rate of clinically-driven target lesion revascularization at 6, 12, 24 and 36 months.
- Patency rate at 12 months post-procedure, defined as freedom from clinically driven TLR and duplex ultrasonography restenosis (ultrasound peak systolic velocity ratio ≤ 2.4 or stenosis ≤50%)
- Rate of vascular access site complication defined as the combined rate of hematoma, AV fistula or a pseudoaneurysm that required intervention, such as surgical repair or transfusion, prolonged hospital stay or required a new hospital admission.
- Lesion success (per device), defined as achievement of a final in-lesion residual diameter stenosis of <50% (by QA), using any device after wire passage through the lesion. Pre- and post-dilatation of the lesion with a non-study device is considered part of assigned device treatment.
- Technical success (per device), defined as achievement of a final in-lesion residual diameter stenosis of <50% (by QA), using the CVT Everolimus-coated PTA Catheter without a device malfunction after wire passage through the lesion. Preand post-dilatation are considered part of assigned device treatment.
- Clinical success (per subject), defined as technical success without the occurrence of major adverse events during the procedure.
- Procedural success (per subject), defined as lesion success without the occurrence of major adverse events during procedure.
- Ankle-Brachial Index (ABI) changes before procedure compared with ABI at discharge and at 6 and 12 months.

Confidential Page 16 of 79

- Change in WIQ (walking impairment questionnaire) from pre-intervention at 6 and 12-months follow-up.
- Change in walking distance from pre-procedure at 6 and 12 months.
- Change in Rutherford classification grades of chronic limb ischemia from preintervention at 6 and 12-months follow-up for the treated limb.

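### Cardiovascular death and limb amputation get no rate of their own, and the secondary MAE rates use a population that can leave out early deaths and bailout subjects

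*Combined protocol and SAP*

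**What the plan says.** Section 3.1 defines MAE as cardiovascular death, amputation of the index limb or ischemia-driven TLR. The primary safety endpoint is freedom from it (ffMAE) at 6 months.

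Section 6.4 gives the analysis: "For both primary endpoints (ffMAE and patency at 6 months), percentages and exact 95% confidence intervals using Clopper-Pearson's method will be calculated". Section 6.3 compares ffMAE with an OPC of 70%.

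Section 3.2 repeats the composite in hospital, at 30 days and at 1, 2 and 3 years. The only component with its own endpoint is TLR: "Rate of clinically-driven target lesion revascularization at 6, 12, 24 and 36 months". TLR is also the only event that 6.4 names for Kaplan-Meier curves. Section 3.9 bases early stopping on the composite MAE rate.

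On populations, 6.2 defines the safety population as enrolled subjects whose procedure was started. The evaluable population further requires that no bailout took place and that there was a valid follow-up visit. Section 6.4 places the primary safety endpoint in the safety population and all secondary endpoints in the evaluable population, there labelled per-treatment.

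**The concern.** A composite count treats a death, a lost limb and a repeat angioplasty as equal. Freedom from ischemia-driven TLR is also part of the primary patency endpoint (3.1), so an anti-restenosis effect improves the safety result directly. A low TLR count can then offset irreversible events one for one, and no planned table would separate them.

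The later safety rates have a second problem. A subject who dies before a valid follow-up visit, or who needs bailout and later has an MAE, does not enter the secondary MAE rates as written.

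This matters because 9.6 calls the trial first-in-human. Its rationale (1.2, 7.4) is a late mortality signal with paclitaxel devices. Subjects are followed for 36 months, yet no mortality rate is planned at any time point.

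**Working it through.** **Inputs from 6.3**
- N: "enrollment of 75 subjects (safety population) will be the recruitment goal".
- OPC: 70% ffMAE.
- Margin: "The assumed difference between the OPC and the treatment group is 15" percentage points, so the alternative is 70% + 15% = 85%.
- Level: "One-tailed α =0.025".
- Not in the documents: separate rates for death, amputation and TLR. These are assumed below, with ranges.

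**1. Reproducing the plan's figures.** Let X be the number free of MAE. The smallest r with P(X ≥ r | 75, 0.70) ≤ 0.025 is 61 (actual level 0.0187). P(X ≥ 61 | 75, 0.85) = 0.853. The plan states: "The power estimates from enrolling 75 subjects to detect 15%-point margins above the Safety and Effectiveness OPCs are 85% and 78%, respectively". The safety figure agrees.

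The Clopper-Pearson limits are the 2.5% quantile of Beta(x, n−x+1) and the 97.5% quantile of Beta(x+1, n−x). The plan's example is "If 11 of 75 (15%) subjects experience MAEs, the point estimate for ffMAE is 85" percent. For 64/75 the limits are 75.3% and 92.4%, as stated there.

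**2. Where the OPC is met.**
- 14 MAEs: 61/75 = 81.3%, interval 70.7% to 89.4%. Met.
- 15 MAEs: 60/75 = 80.0%, interval 69.2% to 88.4%. Not met.

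The type of event plays no part. Four TLRs plus ten deaths or amputations (10/75 = 13.3%, 6.6% to 23.2%) would meet the OPC.

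The stopping criterion is equally blind to type. Section 3.9 gives no number for the anticipated MAE rate. If it is the illustrative 11/75 (an assumption), the upper limit is 24.7%. At full enrolment 18/75 = 24.0% would not exceed that limit and 19/75 = 25.3% would.

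**3. Chance of meeting the OPC.** Let d be the true rate of death or amputation and t the rate of TLR in other subjects, so that each subject counts once. The number of MAEs is Binomial(75, d + t), and the chance is P(MAE ≤ 14).

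| d (assumed) | t = 5% | t = 10% | t = 12% |
|---|---|---|---|
| 3% | 99.9% | 94% | 85% |
| 5% | 99% | 85% | 71% |
| 8% | 94% | 63% | 45% |
| 10% | 85% | 45% | 30% |

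Only the sum matters. For d = 8% and t = 14% the sum is 22%, as for 10% + 12%, so the chance is 30%.

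**4. What component reporting would add.** Against an assumed reference of 1%, 2% or 3% for death or amputation combined, a one-sided 0.025 excess appears at 4, 5 or 7 events. Each count still meets the OPC with up to 14 − 4 = 10, 14 − 5 = 9 or 14 − 7 = 7 further TLR subjects.

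Precision is limited. For 0/75 the upper limit is 1 − 0.025^(1/75) = 4.8%. Against the 1% reference, power is 52% for a true rate of 5% and 86% for 8%.

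**5. Populations, set side by side.**

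| Subject | MAE at 6 months (safety population) | MAE at other times (evaluable population) |
|---|---|---|
| Dies before a valid follow-up visit | Included | Excluded |
| Bailout, later amputation | Included | Excluded |
| No bailout, attends follow-up | Included | Included |

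This takes the per-treatment label in 6.4 to mean the evaluable population of 6.2, the only one defined there with that word.

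**6. Recovering the components by subtraction.** MAE counts ischemia-driven TLR, while the secondary TLR endpoint is clinically-driven. Appendix B defines clinically indicated TLR and does not define the ischemia-driven term. At 6 months the two rates also use different populations. Deaths and amputations therefore cannot be recovered reliably as MAE minus TLR.

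**The case against.** The strongest reply is that the plan does not rest safety on the OPC. Sections 6.1 and 6.3 say that significance is neither required nor enough, put the focus on estimation, and in 6.1 make the absence of safety concerns part of the example. Section 3.2 has separate rates for thrombosis, embolic events and access-site complications. The CEC rules on every death and the Steering Committee reviews safety (10.4), and SAE notification covers death (9.8). Ten deaths or amputations among 75 subjects would be noticed. All of this stands, so a reader who infers that safety is judged only on the OPC goes further than the text. But none of these provisions commits to a rate with an interval, and 6.1 does not define a safety concern.

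A reader might also infer that TLR dominates MAE. No section gives the split. The only death figure is one hazard in Appendix J, at more than 0.1% and less than 1%, and it says nothing about amputation or TLR.

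Nor do the planning values show overlap between safety and patency failures. The 15% MAE and 20% patency failure follow from adding the same 15-point margin to OPCs of 70% and 65%. The overlap comes from the endpoint definitions alone.

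Masking also weakens as TLR rises: at 14% TLR and 8% death or amputation, the OPC is usually missed. Extreme mixes are unlikely if irreversible events are rare: at a true 3%, ten or more in 75 has probability of about 0.0001.

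Finally, 6.4 introduces its binary and time-to-event variables as examples, so component tables are not ruled out. They are not planned either.

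**Conclusion.** The point holds as a gap in planned reporting, together with a wrong population for the secondary safety rates. The OPC can be met with any mix of up to 14 MAEs in 75, and no separate rate for death or amputation would accompany that result. How likely the OPC is to be met despite an excess depends on assumed rates: at 8% death or amputation it runs from 94% (TLR 5%) to 30% (TLR 14%), with components taken as disjoint.

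The population issue needs no assumed rates. It rests on reading the label in 6.4 as the evaluable population of 6.2, and it removes the subjects in whom procedural harm is most likely to appear. The 6-month primary safety analysis is not affected by it.

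This should be corrected before the analysis. It does not undermine the design or the stated safety power. Component rates at this sample size describe harm and cannot establish that it is acceptably low.

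**What to change.** In section 6.4:

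- Analyse MAE at every time point in the safety population.
- Alongside MAE, report counts, percentages and Clopper-Pearson 95% intervals in the safety population for cardiovascular death, all-cause death, index-limb amputation (major and minor, as Appendix B separates them), death or amputation combined, and ischemia-driven TLR.
- Label the component rates as descriptive.
- State whether vascular death counts as cardiovascular death in MAE. Appendix B defines the two separately, and its residual category, non-cardiovascular death, suggests but does not say that vascular deaths are included.

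The cost is a few table rows from data already collected and one clarified definition. The intervals will be wide, and the safety statement will be more cautious.
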